### **12.10. Investigator Responsibilities**

A complete list of Investigator responsibilities are outlined in the clinical trial research agreement and the Statement of Investigator Form FDA 1572, both of which are signed by the Investigator before commencement of the study. In summary, the Investigator will conduct the study according to the current protocol; will read and understand the IB; will obtain IRB/REB/IEC approval to conduct the study; will obtain informed consent from each study participant; will maintain and supply to the Sponsor or designee, auditors and regulatory agencies adequate and accurate records of study activity and drug accountability for study-related monitoring, audits, IRB/REB/IEC reviews and regulatory inspections; will report SAEs to the Sponsor or designee and IRB/ REB/IEC according to the specifics outlined in this protocol; will personally conduct or supervise the study; and will ensure that colleagues participating in the study are informed about their obligations in meeting the above commitments.

### **12.11. Sponsor Responsibilities**

A complete list of the Sponsor responsibilities is outlined in the clinical trial research agreement and in the laws and regulation of the country in which the research is conducted. In summary, the Sponsor will select qualified Investigators, provide them with the information they need to properly conduct the study, ensure adequate monitoring of the study, conduct the study in accordance with the general investigational plan and protocols and promptly inform Investigators, health and regulatory agencies/authorities as appropriate of significant new adverse effects or risks with respect to the drug.

### **12.12. Financial Disclosure**

A separate financial agreement will be made between each Principal Investigator and Pharmacyclics or its authorized representative before the study drug is delivered.

For this study, each Investigator and Subinvestigator (as designated on the Form FDA1572) will provide a personally signed Financial Disclosure Form in accordance with § 21 CFR 54. Each Investigator will notify Pharmacyclics or its authorized representative of any relevant changes in financial disclosure information during the conduct of the study and for 1 year after the study has been completed.

### **12.13. Liability and Clinical Trial Insurance**

In the event of a side effect or injury, appropriate medical care as determined by the Investigator/ designee will be provided.

The ICF will include a description of treatment in the event of a study related injury and handling of the costs associated therewith, incorporating country-specific national regulations and/or local laws. Financial compensation for lost wages, disability or discomfort due to the study is not available.

Clinical trial insurance has been undertaken according to the laws of the countries where the study will be conducted. An insurance certificate will be made available to the participating sites at the time of study initiation.

#### **12.14. Protocol Amendments**

Pharmacyclics will initiate any change to the protocol in a protocol amendment document. The amendment will be submitted to the IRB/REB/IEC together with, if applicable, a revised model ICF. Written documentation of IRB/REB/IEC and required site approval must be received by Pharmacyclics before the amendment may take effect at each site. Additionally under this circumstance, information on any change in risk and/or change in scope must be provided to subjects already actively participating in the study, and they must read, understand and sign each revised ICF confirming willingness to remain in the trial. Any substantial change to the protocol, including any change in risk, must also be approved by the applicable national and/or local regulatory authorities prior to implementation at each site.

No other significant or consistent change in the study procedures, except to eliminate an immediate hazard, shall be effected without the mutual agreement of the Investigator and Pharmacyclics.

#### **12.15. Publication of Study Results**

Pharmacyclics may use the results of this clinical study in registration documents for Regulatory Authorities in the US or abroad. The results may also be used for papers, abstracts, posters, or other material presented at scientific meetings or published in professional journals or as part of an academic thesis by an Investigator. In all cases, to avoid disclosures that could jeopardize proprietary rights and to ensure accuracy of the data, Pharmacyclics reserves the right to preview all manuscripts and abstracts related to this study, allowing Pharmacyclics sufficient time to make appropriate comments before submission for publication.

In most cases, the Investigators at the sites with the highest accruals of eligible subjects shall be listed as lead authors on manuscripts and reports of study results. The Medical Monitor, study director and/or lead statistician may also be included in the list of authors. This custom can be adjusted upon mutual agreement of the authors and Pharmacyclics and in accordance with current standards for authorship as recorded in professional conference and journal submission instructions.

#### **12.16. Study Discontinuation**

The Sponsor reserves the right to terminate the study at any time. Should this be necessary, both the Sponsor and the Investigator will arrange discontinuation procedures. In terminating the study, the Sponsor and the Investigator will assure that adequate consideration is given to the protection of the subjects' interests.

**14. APPENDICES**

**Appendix A. Schedule of Assessments**

Study Visits	Screening Phase	Pre-PD Phase - (1 cycle = 28 days) z						Suspected PD	End-of-Treatment	Post-PD FU
		Cycle 1	Cycles 2-6	Cycles 7-33	Arm A: Cycles 36 - PD (q3 Cycles)	Arm B: Cycles 39 - PD (q6 Cycles) y	As soon as possible after suspected PD			
Study Visit Windows	-30 days	D1 (baseline) a	D2	D8	D15	D1	D1	± 3 days	± 14 days	
Study Drug Administration and Dispensation										
ARM A ibrutinib 420 mg PO + Obinutuzumab 1000 mg IV		ibrutinib: 420 mg PO daily c Obinutuzumab: 1000 mg IV Cycle 1: D1(100 mg), D2 (900 mg), D8 (1000 mg), D15 (1000 mg) Cycle 2 – Cycle 6: D1 (1000 mg)								
ARM Bd Chlorambucil 0.5 mg/kg PO e + Obinutuzumab 1000 mg IV		Chlorambucil: 0.5mg/kg PO e,f Cycle 1 – Cycle 6: D1 & D15 Obinutuzumab: 1000 mg IV Cycle 1: D1(100 mg), D2 (900 mg), D8 (1000 mg), D15 (1000mg) Cycle 2 – Cycle 6: D1 (1000 mg)						ibrutinib: 420 mg PO daily c		
Procedures										
Informed consent	X									
Medical history	X									
Confirm eligibility and randomize g		X								
Patient-reported outcomes (PRO) h	X	X			X		(X)	(X)	X	
Cumulative Illness Rating Scale (CIRS)	X									
Concomitant medications	X	X	X	X	X	X	(X)	(X)	X	
Adverse events i	X	X	X	X	X	X	(X)	(X)	X	
Medical resources usage (MRU)		X	X	X	X	X	(X)	(X)	X	
Study drug compliance review j		X	X	X	X	X	(X)	(X)	X	
Physical exam, vital signs, height, weight, ECOG k	X	X	X l	X	X	X	(X)	(X)	X	

Study Visits	Screening Phase	Pre-PD Phase - (1 cycle = 28 days) z										Suspected PD	End-of-Treatment	Post-PD FU	
		Cycle 1			Cycles 2-6 Every Cycle			Cycles 7-33 Every Odd Cycle							Arm A: Cycles 36 - PD (q3 Cycles)
		D1 (baseline) n	D2	D8	D15	D1	D15	D1	D1	D1	D1				
Study Visit Windows	-30 days														
CT/MRI scan	X m					(X) n,o		(X) o			(X) o				
Bone marrow biopsy/aspirate	X p							(X) p			(X) p				
Overall response assessment q						(X) n		(X) o			(X) o				
Pregnancy	X	X													
Hematology	X	X	X	X	X r	X	X	(X)			(X)	X	X		
Serum chemistry	X	X				X	X	(X) x			(X) x	X	X		
Creatinine clearance (Cockcroft-Gault)	X	X				X	X	(X) x			(X) x	X	X		
Cytogenetics: FISH panel / TP53 assay	X							(X) s				X			
Hepatitis serologies	X														
Coagulation panel	X														
Biomarkers Assays		X				X	X	(X) n			(X) o	X	X		
Flow cytometry blood assays		X				X	X	(X) n			(X) o	X	X		
Infusion reaction cytokines/chemokines t		X													
Genetic/molecular prognostic factors	X														
12-lead ECG u	X														
Survival, including other malignancies															X
Any new anticancer therapy															X
Substudies															
PK sample collection for ARM A only						(X) v	(X) w								

D = day; Term = treatment termination; d/c = discontinuation; PD = progressive disease; FU = follow-up; (x) = not all visits or all subjects

**Footnote:**

- a. C1D1: To be collected pre-dose, unless otherwise specified
- b. End-of-Treatment Visit: may be sooner if subject is scheduled to start a new anticancer treatment. Also, the End-of-Treatment Visit will be performed 30 (± 3) days after discontinuation of therapy (if the assessments do not coincide with regularly scheduled study assessments).
- c. Ibrutinib: Day 1 dose of Cycle 1 should be administered at the investigational site. Subsequent daily doses may be self-administered at home.

- d. For Arm B subjects: if PD is confirmed and the IWCLL treatment guidelines indicate that new anticancer therapy is indicated, second-line treatment plan is established and subsequent assessments are as described in Appendix I.
- e. Chlorambucil: dose based on most recent Day 1-documented weight.
- f. Chlorambucil: Day 1 dose of every cycle (Cycles 1 to 6) and Day 15 dose of Cycle 1 should be taken at the investigational site. Starting on Cycle 2, Day 15 of each cycle may be self-administered at home.
- g. Confirmation of eligibility and randomization may occur within 3 days.
- h. PRO: EQ-5D-5L should be completed prior to any other procedures or physician interactions (after informed consent).
- i. Adverse Events: AEs are reported from the time the subject signs the Informed Consent Form until 30 days following last dose of study drug. In addition to all routine AE reporting, all new malignant tumors including solid tumors, skin malignancies and hematologic malignancies are to be reported as adverse events.
- j. Study Drug Compliance: Includes subject instruction and routine review of study drug diary and evaluation of contents of study drug containers from home administration
- k. Physical Exam: Height will only be taken at the Screening Phase. Vital signs through end of treatment only. ECOG through progressive disease. Review of symptoms should include inquiry of ocular symptoms; subjects should be referred to an ophthalmologist for a formal examination if any Grade  $\geq 2$  symptoms are reported.
- l. Physical Exam: Cycle 1 D8 and D15 will have limited physicals.
- m. CT Scan: Baseline CT scan can be performed up to 6 weeks prior to randomization.
- n. Biomarkers/Flow Cytometry: Cycle 5 only.
- o. CT Scan/Overall Response/Biomarkers/Flow Cytometry: Every 4 cycles after Cycle 5 (Cycles 9, 13, 17, 21, 25, 29, 33), then these will occur every 6 cycles thereafter. If study drug is held before a scheduled response assessment then the response assessment can be delayed up to 4 weeks to allow re-initiation of study drug for 2 weeks (or as long as possible) prior to performing scheduled response assessment.
- p. Bone marrow biopsy and aspirate: should be performed at Screening or up to 90 days before the first dose of study drug, at Cycle 9 (A bone marrow aspirate will not be required at Cycle 9 for subjects who have unequivocal evidence of ongoing gross clinically detectable disease (eg, lymph node >2cm), however these subjects should have a peripheral blood sample sent for MRD analysis and a bone marrow aspirate should be considered for the next scheduled response assessment visit), and as needed to confirm complete response (CR) or evaluate cytopenia. Bone marrow collected to confirm CR should have minimal residual disease (MRD) assessed by flow cytometry on the aspirate; all responders who have an MRD-negative status in the bone marrow, should be followed with peripheral blood MRD analyses every 4 cycles until Cycle 33 then every 6 cycles starting at Cycle 39. All responders who have an MRD-positive status in the bone marrow or peripheral blood, should also be followed with peripheral blood MRD assessments every 4 cycles until Cycle 33 then every 6 cycles starting at Cycle 39. Once the subject becomes MRD-negative in the peripheral blood, this result should be subsequently confirmed with a bone marrow MRD assessment. Additionally, a peripheral blood sample will be taken at Cycle 9.
- q. Overall Response: If study drug is held before a scheduled response assessment then the response assessment can be delayed up to 4 weeks to allow re-initiation of study drug for 2 weeks (or as long as possible) prior to performing scheduled response assessment.
- r. Hematology: Cycles 2-6 Day 15 hematology can be performed locally.
- s. Cytogenetic, FISH panel, and TP53: Assay should be performed at Cycle 9.
- t. Infusion Reaction: Plasma sample will be collected at pre-dose ibrutinib/chlorambucil, immediately prior to infusion of obinutuzumab, and 2 and 4 hours into the obinutuzumab infusion.
- u. ECG: At Screening, 12-lead ECGs will be done *in triplicate* ( $\geq 1$  minute apart). ECG's may be performed at the investigator's discretion, particularly in subjects with arrhythmic symptoms (eg, palpitations, lightheadedness) or new onset of dyspnea.
- v. PK (Arm A only): Cycle 1, Day 15: Pre-dose (window: 30-60 minutes before dose), then 1 hour (window: 45-75 minutes), 2 hours (window: 1.5-2.5 hours), and 4 hours (window: 3.5-4.5 hours) post-dose.

- 
- w. PK (Arm A only): Cycle 2, Day 1: To be collected pre-dose only (window: 30-60 minutes before dose).
  - x. Serum chemistry, including creatinine clearance, will only be taken at Cycles 7, 9, 11, 13, 17, 21, 25, 29, 33, and every 6 cycles until PD.
  - y. Protocol visits for subjects on Arm B will occur every 6 cycles until PD beginning at Cycle 39.
  - z. All subjects randomized to study treatment will continue following all study procedures and visits following the pre-PD schedule until disease progression, including subjects on Arm B who complete treatment and any subjects who discontinue study treatment early.

**Appendix B. ECOG Status Scores**

Status	Eastern Cooperative Oncology Group (ECOG) Performance Status**
0	Fully active, able to carry on all predisease performance without restriction.
1	Restricted in physically strenuous activity but ambulatory and able to carry out work of a light or sedentary nature, eg, light housework, office work.
2	Ambulatory and capable of all self-care, but unable to carry out any work activities. Up and about more than 50% of waking hours.
3	Capable of only limited self-care, confined to bed or chair more than 50% of waking hours.
4	Completely disabled. Cannot carry on any self-care. Totally confined to bed or chair.
5	Dead.

\*\*Oken, MM, et al.1982.

Available at: [http://www.ecog.org/general/perf\\_stat.html](http://www.ecog.org/general/perf_stat.html). Accessed January 4, 2008.

### Appendix C. Inhibitors and Inducers of CYP3A

Inhibitors and inducers of CYP3A are defined as follows. Refer to Section 6.2.1 on instructions for concomitant use of CYP3A inhibitors and inducers with ibrutinib. Further information can be found at the following website: <http://medicine.iupui.edu/clinpharm/ddis/main-table/>.

Inhibitors of CYP3A	Inducers of CYP3A
Strong inhibitors:	carbamazepine
indinavir	efavirenz
nelfinavir	nevirapine
ritonavir	barbiturates
clarithromycin	glucocorticoids
itraconazole	modafinil
ketoconazole	oxcarbazepine
nefazodone	phenobarbital
saquinavir	phenytoin
suboxone	pioglitazone
telithromycin	rifabutin
cobicistat	rifampin
boceprevir	St. John's Wort
mibefradil	troglitazone
telaprevir	
troleandomycin	
Posaconazole a	
Moderate inhibitors:	
aprepitant	
amprenavir	
amiodarone	
atazanavir	
ciprofloxacin	
crizotinib	
darunavir	
dronedarone	
erythromycin	
diltiazem	
fluconazole	
fosamprenavir	
grapefruit juice	
Seville orange juice	
verapamil	
voriconazole a	
imatinib	
Weak inhibitors:	
cimetidine	
fluvoxamine	
All other inhibitors:	
chloramphenicol	
delaviridine	
diethyl-dithiocarbamate	
gestodene	
mifepristone	
norfloxacin	
norfluoxetine	
star fruit	

a. Classification based on internal data.

**Appendix D. Hematologic Adverse Event Grading Scheme (Hallek 2008)**

An evaluation of the hematologic toxicity in patients with advanced CLL/SLL must consider the high frequency of marrow involvement and previous exposure to chemotherapy with consequent medullary compromise at the initiation of therapy. The standard hematologic grading system for solid tumors cannot, therefore, be directly applied. A substantial proportion of patients would be considered to have Grade 2 to 4 hematologic toxicity before any therapy is given. Note that only hematological toxicities deemed Clinically Significant should be recorded as Adverse Events. Therefore, the following modified schema will be used to quantitate hematologic deterioration in patients with CLL/SLL.

**Hematologic Grading Scheme**

Decrease in Platelets or Hgb (Nadir) from Pre-treatment Value, %	ANC/ $\mu$ L (nadir) c	Toxicity Grade
0 - 10% a	$\geq 2000$	0
11 - 24% a,b	$\geq 1500$ and $< 2000$	1
25 - 49% a,b	$\geq 1000$ and $< 1500$	2
50 - 74% a,b	$\geq 500$ and $< 1000$	3
$> 75%$ a,b	$< 500$	4

- a. If at any level of decrease, the platelet count falls below  $20 \times 10^9/L$ , toxicity will be considered Grade 4. If the baseline platelet count is  $< 20 \times 10^9/L$ , platelet toxicity cannot be evaluated.
- b. Baseline and subsequent Hgb values must be determined the day of any given transfusion.
- c. If the ANC was  $< 1000/\mu L$  before therapy, the patient is not evaluable for toxicity referable to the ANC.

**Appendix E. EQ-5D-5L**

*(English version for the UK)*

SAMPLE

UK (English) v.2 © 2009 EuroQol Group. EQ-5D™ is a trade mark of the EuroQol Group

Under each heading, please tick the ONE box that best describes your health TODAY

**MOBILITY**

- I have no problems in walking about
- I have slight problems in walking about
- I have moderate problems in walking about
- I have severe problems in walking about
- I am unable to walk about

**SELF-CARE**

- I have no problems washing or dressing myself
- I have slight problems washing or dressing myself
- I have moderate problems washing or dressing myself
- I have severe problems washing or dressing myself
- I am unable to wash or dress myself

**USUAL ACTIVITIES** (e.g. work, study, housework, family or leisure activities)

- I have no problems doing my usual activities
- I have slight problems doing my usual activities
- I have moderate problems doing my usual activities
- I have severe problems doing my usual activities
- I am unable to do my usual activities

**PAIN / DISCOMFORT**

- I have no pain or discomfort
- I have slight pain or discomfort
- I have moderate pain or discomfort
- I have severe pain or discomfort
- I have extreme pain or discomfort

**ANXIETY / DEPRESSION**

- I am not anxious or depressed
- I am slightly anxious or depressed
- I am moderately anxious or depressed
- I am severely anxious or depressed
- I am extremely anxious or depressed

[figure not shown]
2  
UK (English) v.2 © 2009 EuroQol Group. EQ-5D™ is a trade mark of the EuroQol Group

- We would like to know how good or bad your health is TODAY.
- This scale is numbered from 0 to 100.
- 100 means the best health you can imagine.  
0 means the worst health you can imagine.
- Mark an X on the scale to indicate how your health is TODAY.
- Now, please write the number you marked on the scale in the box below.

YOUR HEALTH TODAY =

The best health  
you can imagine

The worst health  
you can imagine

  
UK (English) v.2 © 2009 EuroQol Group. EQ-5D™ is a trade mark of the EuroQol Group

**Appendix F. Cumulative Illness Rating Scale (CIRS)**

Please take into account that CLL induced illness or organ damage are not included in this rating scale. The goal of this rating scale is to assess comorbidity other than CLL in the patient. If there are two or more illness/impairments of one organ system, the illness/impairment with the highest severity should be evaluated.

Organ system	If illness/impairment present, specify the illness/impairment with highest severity	Score
Cardiac	_____	_____
Hypertension	_____	_____
Vascular	_____	_____
Respiratory	_____	_____
Eye/ear/nose/throat/larynx	_____	_____
Upper gastrointestinal	_____	_____
Lower gastrointestinal	_____	_____
Hepatic/biliary	_____	_____
Renal	_____	_____
Genitourinary	_____	_____
Musculoskeletal	_____	_____
Endocrine/metabolic	_____	_____
Neurological	_____	_____
Psychiatric	_____	_____
	Total score	_____

**CIRS Rating of Comorbidity**

Score		
0	No problem	Organ system not compromised.
1	Mild	Illness/impairment with or without requirement of therapy, excellent prognosis, patient with normal activity
2	Moderate	Illness/impairment requiring therapy, good prognosis; compromised activity of patients
3	Severe	Illness/impairment with urgent requirement for therapy, prognosis unclear, marked restriction in activity of patient.
4	Extremely severe	Life threatening illness/impairment, emergency case of therapy, adverse prognosis.

**Appendix G. Rai Staging**

Rai Stage
0 Lymphocytes (L) in blood (>5000/ $\mu$ L)
I L + enlarged lymph nodes (LN)
II L + spleen and/or liver (LN positive or negative)
III L + anemia (Hgb <11g/dL)
IV L + thrombocytopenia (platelets <100,000/ $\mu$ L)

**Appendix H. New York Heart Association Functional Classification**

Class	Functional Capacity: How a patient with cardiac disease feels during physical activity
I	Patients with cardiac disease but resulting in no limitation of physical activity. Ordinary physical activity does not cause undue fatigue, palpitation, dyspnea or anginal pain.
II	Patients with cardiac disease resulting in slight limitation of physical activity. They are comfortable at rest. Ordinary physical activity results in fatigue, palpitation, dyspnea or anginal pain.
III	Patients with cardiac disease resulting in marked limitation of physical activity. They are comfortable at rest. Less than ordinary activity causes fatigue, palpitation, dyspnea or anginal pain.
IV	Patients with cardiac disease resulting in inability to carry on any physical activity without discomfort. Symptoms of heart failure or the anginal syndrome may be present even at rest. If any physical activity is undertaken, discomfort increases.
Class	Objective Assessment
A	No objective evidence of cardiovascular disease. No symptoms and no limitation in ordinary physical activity.
B	Objective evidence of minimal cardiovascular disease. Mild symptoms and slight limitation during ordinary activity. Comfortable at rest.
C	Objective evidence of moderately severe cardiovascular disease. Marked limitation in activity due to symptoms, even during less-than-ordinary activity. Comfortable only at rest.
D	Objective evidence of severe cardiovascular disease. Severe limitations. Experiences symptoms even while at rest.

**Appendix I. Schedule of Assessments for Subjects Treated with Chlorambucil and Obinutuzumab (Arm B) who are to Receive Next-line Ibrutinib Therapy**

Study Weeks	Assessment for Next-line Ibrutinib Therapy	Treatment Phase d			Follow-up Phase
		Every 4 weeks for 24 weeks	Every 12 weeks until PD	End-of-Treatment Visit	Follow-up (Every 12 weeks)
Study Windows	±14 d	±7 d	±7 d	30 (±3 d)	±7 d
Study Drug Administration					
Ibrutinib 420 mg per day PO		Continuous Daily Dosing			
Procedures					
Medical Monitor approval	x				
Concomitant medications	x	x	x	x	
Adverse events		x	x	x	
Physical examination (including Lymphatic Exam), vital signs, ECOG	x	x	x	x	
Hematology	x	x a	x	x	
Serum chemistry	x				
Investigator assessment of response and for progression b		x	x		
Survival status					x c
Subsequent anticancer therapies					x c
Predictive Biomarkers	x				
CLL=chronic lymphocytic leukemia; d=day(s); ECOG=Eastern Cooperative Oncology Group; IRC=Independent Review Committee; PD=progressive disease; PO=oral; qd=once daily					

- CBC should be performed weekly for the first 4 weeks
- Efficacy assessments should include CT scan every 24 weeks until the first disease progression on protocol. For subjects who have had experienced PD and are crossed over to ibrutinib, CT scans for response assessments may be performed at investigator's discretion.
- Survival and subsequent anticancer therapy status will be collected by telephone
- Subjects will follow the following visit schedule of the Treatment Phase, performing the applicable procedures outlined in the Table on Day 1 of each cycle – Cycle 1 (C1D1, C1D8, C1D15, C1D22 – includes weeks 1, 2, 3, 4 for CBC only), C2 (week 5), C3 (week 9), C4 (week 13), C5 (week 17), C6 (week 21), C7 (week 25), C10 (week 37), C13 (week 49), then continue every 3 cycles (12 weeks) until disease progression or study closure.

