#### *Laboratory*

5. Adequate hematologic function independent of transfusion and growth factor support for at least 7 days prior to Screening and randomization:

- a. Absolute neutrophil count  $\geq 1.0 \times 10^9/L$ .
- b. Platelet count  $> 50 \times 10^9/L$ .
6. Adequate hepatic and renal function defined as:
  - a. Serum aspartate transaminase (AST) or alanine transaminase (ALT)  $\leq 2.5$  x upper limit of normal (ULN).
  - b. Estimated Creatinine Clearance  $\geq 30$  mL/min (Cockcroft-Gault).
  - c. Bilirubin  $\leq 1.5$  x ULN (unless bilirubin rise is due to Gilbert's syndrome or of non-hepatic origin, such as hemolysis).

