#### **5.3.1.6. Dose Modification for Hepatic Impaired Subjects**

Ibrutinib is metabolized in the liver and therefore subjects with clinically significant hepatic impairment at the time of Screening (Child- Pugh class B or C) are excluded from study participation. For subjects who develop mild liver impairment while on study (Child-Pugh class A), the recommended dose reduction for ibrutinib/placebo is to a level of 280 mg daily (two capsules). For subjects who develop moderate liver impairment while on study (Child-Pugh class B), the recommended dose reduction is to a level of 140 mg daily (one capsule). Subjects who develop severe hepatic impairment (Child-Pugh class C) must hold study drug until resolved to moderate impairment (Child-Pugh class B) or better. Monitor subjects for signs of toxicity and follow dose modification guidance as needed (Refer to Appendix J).

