### 8.4. Treatment with Ibrutinib for Subjects on Arm B (Chlorambucil and Obinutuzumab)

Subjects randomized to Arm B who meet the criteria outlined in Section 8.4.1, can receive next-line therapy with ibrutinib and will follow the schedule in Appendix I. Treatment with ibrutinib can be continued until disease progression as determined by the investigator, or until they meet the criteria for withdrawal in Section 9. Subjects must meet all of the criteria for next-line therapy with ibrutinib listed in Section 8.4.1. With Medical Monitor approval, central labs are required to determine appropriateness for next-line ibrutinib.

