#### 8.4.1. Criteria for Next-line Ibrutinib Therapy

1. IRC confirmation of progression and Sponsor approval
2. ECOG Performance Status of  $\leq 3$  (Appendix B)
3. Platelet count  $\geq 25,000/\mu\text{L}$
4. No uncontrolled active systemic fungal, bacterial, viral, or other infection (defined as exhibiting ongoing signs/symptoms related to the infection and without improvement, despite appropriate antibiotics or other treatment)
5. No currently active clinically significant cardiovascular disease such as uncontrolled arrhythmia, congestive heart failure, any Class 3 or 4 cardiac disease as defined by the New York Heart Association Functional Classification (Appendix H), or history of myocardial infarction within 6 months prior to first dose with study drug
6. Recovered from the acute toxicities due to prior chemotherapy, radiotherapy, investigational drugs, or experimental treatments (non-hematologic toxicities have resolved to a NCI CTCAE [version 4.03] Grade of  $\leq 2$ )
7. No known Richter's transformation
8. Does not require or receive anticoagulation with warfarin or equivalent vitamin K antagonists (eg, phenprocoumon)
9. Male and female subjects of reproductive potential who agree to use highly effective methods of birth control (eg, condoms, implants, injectables, combined oral contraceptives,

some intrauterine devices [IUDs], complete abstinence, or sterilized partner) during the period of therapy and for 90 days after the last dose of ibrutinib, chlorambucil or obinutuzumab, and at least 18 months after the last obinutuzumab dose for female subjects. Post menopausal females (>45 years old and without menses for >1 year) and surgically sterilized females are exempt from this criterion

10. No history of stroke or intracranial hemorrhage within 6 months

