#### **8.4.2. Next-line Ibrutinib Therapy Treatment Phase**

Refer to the next-line ibrutinib therapy Schedule of Assessments (Appendix I) for a complete list of procedures to be performed at each scheduled study visit.

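### Appendix I schedules serum chemistry only before crossover, so Arm B subjects have none scheduled while on next-line ibrutinib, although 5.3.1.6 sets dose changes for hepatic impairment arising on study

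*Protocol*

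**What the plan says.** Three places in the Protocol move crossover subjects onto Appendix I, titled "Schedule of Assessments for Subjects Treated with Chlorambucil and Obinutuzumab (Arm B) who are to Receive Next-line Ibrutinib Therapy". Section 8.4 says that they "can receive next-line therapy with ibrutinib and will follow the schedule in Appendix I". Section 8.4.2 reads "Refer to the next-line ibrutinib therapy Schedule of Assessments (Appendix I) for a complete list of procedures to be performed". Appendix A, footnote d, says that once next treatment is indicated a "second-line treatment plan is established and subsequent assessments are as described in Appendix I". The Appendix A schedule stops applying at IRC-confirmed progression (8.2), which is also the entry condition for crossover (8.4.1, item 1).

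The Appendix I visit footnote has subjects "performing the applicable procedures outlined in the Table on Day 1 of each cycle", on a stated list of cycles. In the table, serum chemistry is marked once, in the pre-crossover column. Hematology is marked in four columns: pre-crossover, every 4 weeks for 24 weeks, every 12 weeks, and End-of-Treatment. The only laboratory footnote adds weekly blood counts in the first 4 weeks.

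Section 5.3.1.6 covers hepatic impairment that develops on study. It recommends 280 mg for Child-Pugh class A and 140 mg for class B. For class C it is mandatory: "Subjects who develop severe hepatic impairment (Child-Pugh class C) must hold study drug until resolved to moderate impairment". Scoring follows Appendix J. Bilirubin, albumin, AST, ALT and creatinine belong to the chemistry panel (7.1.2.2). PT/INR is scheduled at Screening only (7.1.2.3).

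**The concern.** The same drug at the same continuous dose has regular chemistry in Arm A and none scheduled on treatment after crossover, and the Protocol gives no reason for the difference. A site that follows Appendix I exactly would not measure bilirubin or albumin after the pre-crossover sample, however long ibrutinib continues. Impairment without clinical signs would then have no scheduled trigger, and a 5.3.1.6 dose change could come late or vary between sites.

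The Protocol itself shows why exposure matters once impairment exists: section 1.2.2.1 reports single-dose ibrutinib AUC 2.7-, 8.2- and 9.8-fold higher in mild, moderate and severe hepatic impairment. Those ratios do not say how often impairment would arise.

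Crossover entry does not fill the gap. Central laboratory results and approval are required (8.4, 8.4.1), but 8.4.1 lists no AST/ALT, bilirubin or Child-Pugh limit. Item 6 asks for subjects "Recovered from the acute toxicities due to prior chemotherapy, radiotherapy, investigational drugs, or experimental treatments", with non-hematologic toxicity at Grade 2 or lower. At randomization, by contrast, the criterion "Adequate hepatic and renal function defined as" set numerical limits (4.1, item 6). In any case, one sample before treatment cannot detect what develops later.

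**Working it through.** The plan states no figure on this point, so the check is a count of scheduled tests, followed by a check of what chemistry can contribute to the Child-Pugh score.

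**Crossover (Appendix I and its visit footnote).** Day 1 visits through week 49 are C1, C2, C3, C4, C5, C6, C7, C10 and C13, which is 9 visits spanning (13 − 1) × 28 = 336 days. Hematology is scheduled at all 9 and chemistry at 0. Leaving out the first-dose visit, it is 0 of 8.

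**Arm A over the same 13 cycles.** Chemistry is listed at C1 Day 1 (8.2.1.1), at Day 1 of C2 to C6 (8.2.1.2), and at C7, C9, C11 and C13 (8.2.1.3): 1 + 5 + 4 = 10. Removing the pre-dose C1 sample leaves 9.

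**Arm A on ibrutinib alone.** Obinutuzumab ends at Cycle 6, so this is a milder comparison. From C7 to C19, 12 × 28 = 336 days, chemistry falls at C7, C9, C11, C13 and C17: 5 samples, longest gap (17 − 13) × 28 = 112 days. The contrast remains, 5 against 0.

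**What the missing samples feed.** Appendix J scores five items:

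| Item | Scheduled on treatment, crossover | Scheduled on treatment, Arm A |
|---|---|---|
| Bilirubin | No | Yes |
| Albumin | No | Yes |
| PT/INR | No | No |
| Ascites | By examination | By examination |
| Encephalopathy | By examination | By examination |

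Two of five items are therefore available from scheduled crossover procedures and four of five in Arm A. AST, ALT and creatinine are also unscheduled after crossover, but they are general safety tests and do not enter the score.

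**How far chemistry alone can move the class.** With all five items normal the score is 5, already within class A (5–6), so chemistry by itself does not mark the onset of class A. Hold PT/INR, ascites and encephalopathy at 1 point each, 3 in total. Class B (7–9) then needs at least 4 points from bilirubin and albumin together: 2 + 2, 3 + 1 or 1 + 3 as a minimum. The most they can give is 3 + 3, for a score of 9, still class B. Class C (10 or more) therefore also needs an abnormal PT/INR or a clinical sign. Scheduled chemistry mainly serves silent class B impairment and prompts the PT/INR that completes the score.

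**End-of-Treatment.** The texts do not agree. Appendix I leaves the chemistry cell blank. The synopsis gives all subjects an End-of-Treatment Visit, including after crossover ibrutinib, and 8.2.2 lists chemistry at that visit. But 8.2.2 sits under the pre-progression phase. On either reading the visit follows discontinuation and cannot guide dosing.

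**The case against.** The strongest reply is that a schedule sets a minimum. Sites may test whenever they see cause, 5.3.1.6 asks them to watch for toxicity, and adverse events and a physical examination (skin, eyes, abdomen and nervous system among its components, 7.1.1.6) are scheduled throughout crossover treatment. A lighter schedule after progression also looks deliberate: CT becomes discretionary, and the SAP's treatment-emergent period closes before crossover ibrutinib, so crossover values fall outside the default laboratory summaries (SAP section 5). Hepatotoxicity has no heading of its own in the ibrutinib risk list in 1.2.4. Finally, PT/INR is not repeated in either arm, so even Arm A cannot be fully scored from scheduled tests.

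Much of this stands and limits the point. The PT/INR gap is common to both arms, the class A and B reductions are recommendations, and no frequency of harm can be shown. It does not explain why bilirubin and albumin are scheduled for ibrutinib subjects in one setting and not the other. Examination also does not detect impairment that is still biochemical.

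A reader might infer that crossover subjects have no hepatic safeguard, or that chemistry is ruled out at End-of-Treatment. The documents support neither: clinical monitoring and unscheduled testing remain, and the synopsis with 8.2.2 can be read to include the End-of-Treatment sample. A reader might also infer that the class C hold cannot be triggered. It can, because class C needs an abnormality beyond bilirubin and albumin, which may itself be visible clinically.

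**Conclusion.** The point holds as a minor patient-safety monitoring gap. Appendix I governs crossover and schedules no serum chemistry on ibrutinib: 0 of 9 Day 1 visits through week 49, against 9 post-first-dose samples in Arm A over the same 13 cycles, or 5 in an equal period of Arm A on ibrutinib alone. The practical loss is two of the three Child-Pugh laboratory items, plus AST/ALT and creatinine as general safety tests.

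This rests on two readings. First, Appendix I replaces Appendix A after confirmed progression, as 8.4, 8.4.2 and footnote d indicate. Second, 5.3.1.6 applies to crossover ibrutinib; it speaks of impairment arising on study, and no separate crossover dose rule is given.

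The documents give neither the proportion crossing over nor a rate of hepatic events, so the number of subjects affected cannot be estimated. It would be wrong to carry this over to the trial's conclusions: crossover follows the IRC-confirmed progression that already counts as the PFS event, so the PFS analysis, power and alpha are untouched.

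**What to change.** In Appendix I, mark serum chemistry at Day 1 hematology draws that already exist, for example C2, C3, C5, C7, C10 and C13, then every 12 weeks, and at End-of-Treatment, which also settles the ambiguity there. Starting at C2 matches the first post-dose chemistry in Arm A (8.2.1.2). This gives 6 samples in 336 days, with gaps from C1 of 28, 28, 56, 56, 84 and 84 days; the longest is 84 days, against 112 in Arm A on ibrutinib alone.

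State that PT/INR is obtained, in either arm, when bilirubin or albumin is abnormal, so that the Child-Pugh score can be completed. The doses in 5.3.1.6 need no change.

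The cost is one added sample at 6 existing draws in the first 49 weeks, one every 12 weeks after that, one at End-of-Treatment, and an occasional PT/INR. No visits are added.

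A separate minor correction can go into the same amendment: from Cycle 36, 8.2.1.4 puts Arm A chemistry every 3 cycles, while Appendix A footnote x says every 6 cycles after Cycle 33. The next sample falls at (36 − 33) × 28 = 84 or (39 − 33) × 28 = 168 days, depending on the text followed. One interval should be chosen.
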